6.1.2. AEs and SAEs

6.1.2.1. Main Analysis

- Estimand: The proportion of participants reporting AEs from vaccination through 4 weeks after vaccination and SAEs from vaccination through 6 months after vaccination (Section 2.2).
- Analysis set: Safety population (Section 4).

- Analysis time point: From vaccination through 4 weeks after vaccination for AEs and from vaccination through 6 months after vaccination for SAEs (Section 3.1).
- Analysis methodology: 95% CI of the proportion of participants reporting each AE/SAE using the Clopper-Pearson method (Section 5.2.1).
- Intercurrent events and missing data: Missing values will not be imputed except for partially missing dates (Section 5.3).
- Reporting results: Descriptive statistics, including counts, point estimates, and the associated exact 2-sided 95% CIs using the Clopper-Pearson method, for the proportion of participants reporting AEs from vaccination through 4 weeks after vaccination for each vaccine group, for participants 18 through 64 years of age.
- Reporting results: Descriptive statistics, including counts, point estimates, and the associated exact 2-sided 95% CIs using the Clopper-Pearson method, for the proportion of participants reporting SAEs from vaccination through 6 months after vaccination for each vaccine group, for participants 18 through 64 years of age.

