8.4.7. Adverse Events of Special Interest

The following events are considered AESIs:

For Substudy A:

- A confirmed diagnosis of influenza.
- Confirmed diagnosis of myocarditis or pericarditis occurring within 4 weeks after vaccination. See Section 10.11.8.8.10.
- Confirmed COVID-19 diagnosis after Visit 1 through the end of the study (clinical signs/symptoms per CDC²⁸ and positive SARS-CoV-2 NAAT or rapid antigen test result).

For Substudy B:

- A confirmed diagnosis of influenza.
- Confirmed diagnosis of myocarditis or pericarditis occurring within 6 weeks after vaccination. See Section 10.12.8.12.
- Confirmed COVID-19 diagnosis after Visit 201 through the end of the study (clinical signs/symptoms per CDC²⁸ and positive SARS-CoV-2 NAAT or rapid antigen test result) (excluding Group 12).
- Potential menstrual cycle disturbances. See Section 10.12.8.11.

AESIs are examined as part of routine safety data review procedures throughout the clinical trial and as part of signal detection processes. Should an aggregate analysis indicate that these prespecified events occur more frequently than expected, eg, based on epidemiological data, literature, or other data, then this will be submitted and reported in accordance with Pfizer's safety reporting requirements. Aggregate analyses of safety data will be performed on a regular basis per internal SOPs.

All AESIs must be reported as an AE or SAE following the procedures described in Section 8.4.1 through 8.4.4. An AESI is to be recorded as an AE or SAE on the CRF. In addition, an AESI that is also an SAE must be reported using the Vaccine SAE Report Form.

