assist the participant with downloading the application or issue						
provisioned device if required						
Provide thermometer and measuring device		X				
Review reactogenicity e-diary data (daily review is optimal						
during the active diary period)		ţ		*		
Review ongoing reactogenicity e-diary symptoms and obtain stop				X	X	
dates						
Collect AEs and SAEs as appropriate ^{f,d}	X	X	X	X	X	X
Collect e-diary or assist the participant with deleting application				X	X	

- a. Visit may be completed as a home health visit (see Section 10.12.8.2).
- b. Visit will be completed as a telehealth visit (see Section 10.12.8.1).
- c. Including, if indicated, a physical examination.
- d. Prior to vaccination at Visit 201.
- e. Only up to 20 participants in Groups 3, 4, and 5 will have 50 mL drawn (see Section 10.12.4.1).
- f. AEs are collected from the completion of informed consent through Visit 204. SAEs are collected from the completion of informed consent through the end of study participation. Additionally, any AEs occurring up to 48 hours after blood draws at Visit 204 must be recorded.

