Any female study participant who reports any symptoms that may indicate a disturbance of their normal menstrual cycle (including, but not exclusively, heavy menstrual bleeding, amenorrhea, and irregular periods) following receipt of study intervention until 6 months after the first vaccination should be specifically evaluated by the investigator. Details of the symptoms, menstrual history, and results of any investigations performed will be recorded in the CRF.

10.12.8.11.1. Unscheduled Visit for a Grade 3 or Suspected Grade 4 Reaction for Substudy B

If a Grade 3 local reaction (Section 8.3.5.2), systemic event (Section 8.3.5.3), or fever (Section 8.3.5.4) is reported in the reactogenicity e-diary, a telephone contact should occur to ascertain further details and determine whether a site visit is clinically indicated. If a suspected Grade 4 local reaction (Section 8.3.5.2), systemic event (Section 8.3.5.3), or fever (Section 8.3.5.4) is reported in the reactogenicity e-diary, a telephone contact or site visit should occur to confirm whether the event meets Grade 4 criteria.

A site visit must be scheduled as soon as possible to assess the participant unless any of the following is true:

- The participant is unable to attend the unscheduled visit.
- The local reaction/systemic event is no longer present at the time of the telephone contact.
- The participant recorded an incorrect value in the reactogenicity e-diary (confirmation of a reactogenicity e-diary data entry error).
- The PI or authorized designee determined it was not needed.
- This telephone contact will be recorded in the participant's source documentation and the CRF.

If the participant is unable to attend the unscheduled visit, or the PI or authorized designee determined it was not needed, any ongoing local reactions/systemic events must be assessed at the next study visit.

During the unscheduled visit, the reactions should be assessed by the investigator or a medically qualified member of the study staff, such as a study physician or a study nurse, as applicable to the investigator's local practice, who will:

- Measure oral temperature (°F/°C).
- Measure minimum and maximum diameters of redness (if present).

- Measure minimum and maximum diameters of swelling (if present).
- Assess injection site pain (if present) in accordance with the grades provided in Section 8.3.5.2.
- Assess systemic events (if present) in accordance with the grades provided in Section 8.3.5.3.

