6.1.2.2. Sensitivity/Supplementary Analysis

The proportion of participants reporting AEs (which includes reactogenicity events collected in the AE CRF during the e-diary collection period) from vaccination through 4 weeks after vaccination will be provided as a sensitivity analysis.

Additional analyses will include summaries of AE/SAEs by SOC and PT. Furthermore, descriptive summaries may be done for different types of AEs (eg, related AEs, severe AEs, immediate AEs, AEs leading to discontinuations, etc). Additionally, any AEs occurring up to 48 hours after the blood draws at the 4-week follow-up visit will be summarized descriptively or included in the listing.

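### The Substudy B SAP commits to no AESI summary, so nonserious menstrual cycle disturbances recorded after week 4 have no planned output and earlier ones are reported over a denominator that includes men

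*SAP*

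**What the plan says.** **Protocol.** Section 8.4.7 includes among the Substudy B AESIs: "Potential menstrual cycle disturbances. See Section 10.12.8.11". Section 10.12.8.11 covers any female participant with symptoms suggesting a disturbed cycle "following receipt of study intervention until 6 months after the first vaccination should be specifically evaluated by the investigator", and adds: "Details of the symptoms, menstrual history, and results of any investigations performed will be recorded in the CRF". Section 10.12.8.13 repeats this and places the evaluation at the next planned visit. On recording, section 8.4.7 says: "An AESI is to be recorded as an AE or SAE on the CRF". Footnote f of the Substudy B schedule of activities (10.12.1) says: "AEs are collected from the completion of informed consent through Visit 204".

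**Substudy B SAP.** Section 6.1.2.1 gives the AE period as "From vaccination through 4 weeks after vaccination for AEs" and the SAE period as "from vaccination through 6 months after vaccination for SAEs". Section 6.1.2.2 commits to summaries by system organ class and preferred term and then continues: "Furthermore, descriptive summaries may be done for different types of AEs (eg, related AEs, severe AEs, immediate AEs, AEs leading to discontinuations, etc". AESIs are not named there, nor in the endpoints, safety summaries or abbreviation list. The safety population (section 4) is everyone vaccinated, and section 6.3 rules out subsets by sex. Section 2.1 declares no modification of the protocol's analysis plan.

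**Substudy A SAP, for contrast.** Section 3.1.4 derives an AESI variable, and section 6.1.2.2 lists AESIs among the endpoints that will be summarized.

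**The concern.** The sponsor singled out menstrual disturbances for monitoring in Substudy B, gave them a 6-month window and asked for details in the CRF. The SAP then provides no place for most of that window unless the event is serious. Within the first 4 weeks, related terms such as heavy bleeding, amenorrhea and irregular periods would be spread over separate preferred-term rows, each divided by a group total that includes men.

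Protocol 8.4.7 frames its own signal check as whether prespecified events occur more often than expected. That is a question about frequency, so it needs a count over the full window and a denominator of people who can have the event. Without a committed table, a reader of the study report could not compare vaccine groups on this AESI, although the data would be in the CRF.

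**Working it through.** **1. Where would a nonserious menstrual disturbance appear?** Outputs in the Substudy B SAP:

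| Output | Onset to week 4 | Onset after week 4 |
|---|---|---|
| AE proportion (6.1.2.1) | counted within all AEs | outside the period |
| SOC and preferred-term summaries (6.1.2.2) | separate preferred terms | no period of their own is given; I take the 4-week AE period |
| SAE proportion (6.1.2.1) | no (serious only) | no (serious only) |
| AEs within 48 hours of the Visit 204 blood draw (6.1.2.2) | only if in that interval | only if in that interval |
| Optional AE types (6.1.2.2) | permitted, AESIs not named | none committed |
| Myocarditis/pericarditis symptoms (6.4.1, 6.5) | not relevant | not relevant |

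Apart from the short interval around the Visit 204 draw, the right-hand column is empty.

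**2. Length of the gap.** Visit 204 falls 26 to 30 days after vaccination and Visit 205 at 175 to 189 days (10.12.1).

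- Smallest covered share: 26/189 = 13.8%.
- Largest covered share: 30/175 = 17.1%.

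So about 83% to 86% of the menstrual window has no planned analysis of nonserious events. This is calendar time only. It does not mean that 83% to 86% of events are missed, because ascertainment differs before and after Visit 204.

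**3. Denominator.** Printed percentage = cases/all vaccinated = (cases/women) × (women/all vaccinated). The documents give no share of women; 30% to 60% is my assumption. Examples, with Clopper-Pearson 95% CIs:

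| Group size | Assumed women | Cases | Over women | Over all vaccinated |
|---|---|---|---|---|
| 30 | 9 (30%) | 2 | 22.2% (2.8 to 60.0) | 6.7% (0.8 to 22.1) |
| 30 | 15 (50%) | 3 | 20.0% (4.3 to 48.1) | 10.0% (2.1 to 26.5) |
| 30 | 18 (60%) | 4 | 22.2% (6.4 to 47.6) | 13.3% (3.8 to 30.7) |
| 120 | 60 (50%) | 12 | 20.0% (10.8 to 32.3) | 10.0% (5.3 to 16.8) |

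The printed figure is 0.3 to 0.6 of the rate in women, an understatement of 1/0.6 = 1.7-fold to 1/0.3 = 3.3-fold. The case count is the same in both columns.

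**4. The plan's own figures.** Protocol Table 9 gives the chance of seeing at least one event, 1 − (1 − p)^n. For p = 5%:

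- n = 30: 1 − 0.95^30 = 78.5%, as printed.
- n = 120: 1 − 0.95^120 = 99.8%, as printed.

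The other cells also reproduce, except that n = 120 at 7% is 99.98% and is printed as above 99.99%, which has no bearing here. For an event that only women can have, n is the number of women. With 9 to 18 women the chance at 5% is 37% to 60%; with 36 to 72 women it is 84.2% to 97.5%.

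**5. Are nonserious events after Visit 204 recorded at all?** The protocol gives two answers.

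- Section 8.4.1 and the 10.12.1 footnote end nonserious AE collection at Visit 204, apart from events within 48 hours of the Visit 204 blood draw. Section 10.12.8.9.6 asks only for SAEs at Visit 205.
- Section 10.12.8.1 asks for AEs as well as SAEs at the final telehealth contact. Sections 10.12.8.11 and 10.12.8.13 require menstrual evaluation and CRF entry to 6 months.

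After week 4, the next planned visit in 10.12.8.13 can only be that telephone contact.

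**The case against.** The strongest reply is that the 4-week limit is not the SAP's invention. It repeats the protocol's primary estimand (10.12.3), and the protocol itself is unclear on whether nonserious events are collected later. This stands. The problem is not SAP wording alone, and any count after week 4 would rest on incomplete ascertainment.

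Other points also stand in part:

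- The open-ended list in 6.1.2.2 permits an AESI summary. It does not commit to one or name AESIs.
- Protocol 8.4.7 provides for aggregate AESI review under internal procedures. That is outside the SAP and is not a specified analysis by vaccine group.
- The Substudy A SAP summarizes AESIs with the population and presentation of its main AE analysis. It supports a committed AESI summary, but not a 6-month window or a female denominator.
- All-vaccinated denominators follow protocol 10.12.9.3.2, the counts are shown, and the substudy is descriptive. With about 30 per group, even the corrected intervals are wide.

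A reader might infer more than the documents support:

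- *No AESI is analysed at all.* Myocarditis and pericarditis symptoms within 4 weeks are summarized (SAP 6.4.1 and 6.5), and protocol 10.12.8.10 has any such diagnosis reported as an SAE, which brings it into the 6-month analysis.
- *Every menstrual event after week 4 goes unreported.* Serious ones are in the SAE analysis.
- *Women of childbearing potential are the natural denominator.* Protocol 10.5.3 places premenopausal women with bilateral salpingectomy outside that class although they may menstruate, while 10.12.8.11 covers any female participant. Cases could then fall outside their own denominator.

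**Conclusion.** The point holds in a limited form. The Substudy B SAP commits to no AESI summary. Nonserious menstrual disturbances recorded after week 4 have no planned table or listing, and those up to week 4 appear ungrouped over a denominator that includes men.

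The direction of the understatement is certain whenever a group contains men. Its size, 0.3 to 0.6 of the rate in women, rests wholly on the assumed 30% to 60% share of women. Any fixed fold-understatement quoted as a property of this trial would be unsupported.

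Confirmed COVID-19, an AESI through the end of the study (excluding Group 12), has the same gap for nonserious cases after week 4. For myocarditis and pericarditis, the AESI window is 6 weeks and the symptom summaries stop at 4.

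No hypothesis test or primary estimand is affected. What is lost is by-group reporting of a harm chosen for monitoring, which makes this worth correcting before the final analysis.

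**What to change.** **SAP.** In section 6.1.2.2 of the Substudy B SAP, replace the optional wording with a committed AESI table and listing, by vaccine group and pooled, using each AESI's own window from protocol 8.4.7. For menstrual cycle disturbances:

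- take the window to 6 months from 10.12.8.11, grouping the relevant preferred terms;
- use female participants in the safety population as the denominator, or those who menstruate if that status is an analysable CRF field, with Clopper-Pearson CIs;
- show events to week 4 and after week 4 separately, and footnote the later ones as not systematically collected.

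Across all 630 planned participants, the pooled female denominator would be 0.3 × 630 = 189 to 0.6 × 630 = 378 under the same assumed shares.

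**Protocol.** Reconcile 8.4.1, the 10.12.1 footnote and 10.12.8.9.6 with 10.12.8.1, 10.12.8.11 and 10.12.8.13 on recording nonserious events after Visit 204. Which rule should apply is for the sponsor to settle; the SAP should then state how those data are handled.

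**Cost.** One SAP paragraph, one table and one listing, plus a protocol clarification. Sex is already collected and the menstrual details are already required in the CRF, so the table itself needs no new visits or samples. The downside is small counts and incomplete ascertainment after week 4.

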6.1.2.2. Sensitivity/Supplementary Analysis

The proportion of participants reporting AEs (which includes reactogenicity events collected in the AE CRF during the e-diary collection period) from vaccination through 4 weeks after vaccination will be provided as a sensitivity analysis.

Additional analyses will include summaries of AE/SAEs by SOC and PT. Furthermore, descriptive summaries may be done for different types of AEs (eg, related AEs, severe AEs, immediate AEs, AEs leading to discontinuations, etc). Additionally, any AEs occurring up to 48 hours after the blood draws at the 4-week follow-up visit will be summarized descriptively or included in the listing.

6.1.3. Laboratory Data

6.1.3.1. Main Analysis

- Estimand: The proportion of participants reporting abnormal troponin I laboratory values for each study intervention group at 2 days and 1 week after vaccination (Section 2.2).
- Analysis set: Safety population (Section 4).
- Analysis time point: At 2 days (visit window 2 to 4 days) and 1 week (visit window 6 to 8 days) after vaccination (Section 3.1).
- Analysis methodology: 95% CI of the proportion of participants reporting abnormal troponin I laboratory values using the Clopper-Pearson method (Section 5.2.1).

- Intercurrent events and missing data: Missing values will not be imputed.
- Reporting results: Descriptive statistics, including counts, point estimates, and the
 associated exact 2-sided 95% CIs using the Clopper-Pearson method, for the proportion
 of participants reporting abnormal troponin I laboratory values for each vaccine group at
 2 days and 1 week after vaccination (within windows), for participants 18 through 64
 years of age.

6.1.3.2. Sensitivity/Supplementary Analysis

Not applicable.

6.1.4. ECG Data

6.1.4.1. Main Analysis

- Estimand: The proportion of participants reporting new ECG abnormalities for each study intervention group at 2 days and 1 week after vaccination (Section 2.2).
- Analysis set: Safety population (Section 4).
- Analysis time point: At 2 days (visit window 2 to 4 days) and 1 week (visit window 6 to 8 days) after vaccination (Section 3.1).
- Analysis methodology: 95% CI of the proportion of participants reporting new ECG abnormalities using the Clopper-Pearson method (Section 5.2.1).
- Intercurrent events and missing data: Missing values will not be imputed.
- Reporting results: Descriptive statistics, including counts, point estimates, and the associated exact 2-sided 95% CIs using the Clopper-Pearson method, for the proportion of participants reporting new ECG abnormalities for each vaccine group at 2 days and 1 week after vaccination (within windows), for participants 18 through 64 years of age.

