10.12.8.6. Clinical Safety Laboratory Assessments for Substudy B

Please see Section 8.3.4. Additionally, see Section 10.2 for the list of clinical safety laboratory tests to be performed and the SoA for the timing and frequency.

10.12.8.7. Stopping Rules for Substudy B Groups 2, 6, 7, 8, 9, 10, 11, and 12

The following stopping rules are in place for participants receiving one of the following combinations, not previously covered in Substudy A: qIRV/bivalent BNT162b2 (original/Omi BA.4/BA.5), tIRV/bivalent BNT162b2 (original/Omi BA.4/BA.5), or bIRV/bivalent BNT162b2 (original/Omi BA.4/BA.5) concurrently with licensed QIV in Substudy B, based on AE, ECG, and laboratory data review. These data will be reviewed on an ongoing basis by the investigator (or medically qualified designee) and sponsor in order to promptly identify and flag any event that potentially contributes to a stopping rule.

The sponsor study team will be unblinded, so will be able to assess whether or not a stopping rule has been met on the basis of a participant's individual study intervention allocation.

In the event that sponsor personnel confirm that a stopping rule is met, the following actions will commence:

- The IRC will review all appropriate data.
 - The stopping rule will PAUSE randomization and study intervention administration in all vaccine groups across both age strata
 - For all participants already vaccinated, all other routine study conduct activities, including ongoing data entry, reporting of AEs, participant e-diary completion, blood sample collection, and participant follow-up, will continue during the pause.

A stopping rule is met if any of the conditions listed in the stopping rule criteria below occur within 4 weeks after study intervention administration. Each vaccine group will be evaluated for contribution to stopping rules independently.

Stopping Rule Criteria:

- If any vaccinated participant develops:
 - A new ECG abnormality that a cardiologist judges consistent with probable or possible myocarditis or pericarditis, including but not limited to:
 - Sustained atrial or ventricular arrhythmias
 - Second-degree Mobitz Type II or worse AV block, new bundle branch block
 - Diffuse ST-segment elevation or PR-segment inversion, compatible with pericarditis
 - An abnormal troponin I value that is confirmed abnormal on repeat testing, assessed as related to study intervention by the investigator.

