6.1.3. Laboratory Parameters

6.1.3.1. Main Analysis

- Estimand strategy: Treatment policy (Section 2.2.1).
- Analysis set: Safety population (Section 4).
- Analysis methodology: Descriptive summary statistics (Section 5.2.1).
- Analysis timing: Within 2 to 4 and within 6 to 8 days after vaccination.
- Intercurrent events and missing data: All data collected are included. Missing dates/laboratory values will be imputed as described in Pfizer's Vaccine Statistics Rulebook.
- Reporting results: The number of participants with abnormal troponin I laboratory values within the visit window at Visits 2 and 3 after vaccination (n), proportion, and associated 2-sided Clopper-Pearson 95% CI will be presented by study intervention group, for participants 18 through 64 years of age and ≥65 years of age separately and combined.

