6.1.4.2. Sensitivity/Supplementary Analysis

Not applicable.

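### Substudy B's troponin and ECG rates count only in-window results, so a late abnormal result is missing from the named rate; Substudy A's troponin text contradicts itself on the same point

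*SAP*

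**What the plan says.** **Substudy B, ECG (SAP B 6.1.4.1).** The time points are given as "At 2 days (visit window 2 to 4 days) and 1 week (visit window 6 to 8 days) after vaccination". The reported estimate is "for the proportion of participants reporting new ECG abnormalities for each vaccine group at 2 days and 1 week after vaccination (within windows"). On missing data the section says "Intercurrent events and missing data: Missing values will not be imputed". The sensitivity section that follows (6.1.4.2) reads "Not applicable".

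**Substudy B, troponin (SAP B 6.1.3.1).** The same windows apply, and the rate is again reported at "2 days and 1 week after vaccination (within windows), for participants 18 through 64" years of age. Section 6.1.3.2 plans no sensitivity analysis either.

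**Substudy A, troponin (SAP A 6.1.3.1).** The strategy is treatment policy in the safety population, and the data rule is "All data collected are included". The reporting line in the same section is "The number of participants with abnormal troponin I laboratory values within the visit window at Visits 2 and 3 after vaccination (n"), with the timing given as the same two windows.

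**Substudy A, ECG.** No window filter is applied. SAP A 6.1.4.1 counts new abnormalities cumulatively up to Visits 2 and 3, and Protocol 10.11.9.3.5.1 adds a count of any new ECG abnormality after vaccination.

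**Stopping rules.** For the novel Substudy B groups, Protocol 10.12.8.7 says: "A stopping rule is met if any of the conditions listed in the stopping rule criteria below occur within 4 weeks after study intervention administration". Substudy A (10.11.8.6) also uses 4 weeks for its combination groups.

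**The concern.** A safety rate should count the abnormal results that were obtained. Here the count depends on whether the visit kept to schedule. Protocol 7.3 tells sites to rebook a missed visit as soon as possible, so late visits are foreseeable. A Visit 202 held 5 days after vaccination still yields a valid central troponin and ECG, yet both fall between the two windows. The same happens to a Visit 203 held on day 9.

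A window filter of this kind belongs to a per-protocol analysis. SAP A 2.2.2 lists out-of-window blood collection as an excluding event for immunogenicity, but the safety estimands in SAP A 2.2.1 do not. The immunogenicity draw is even given slack: both SAPs accept 26 to 35 days against a 26 to 30 day visit window. The cardiac results get none.

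Abnormal troponin and new ECG abnormalities are named primary safety endpoints, and most groups have 30 participants. One uncounted event can be the difference between a row with a signal and a row that reads zero.

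**Working it through.** **Step 1: which days count.** All days are counted after vaccination. The windows cover {2, 3, 4} and {6, 7, 8}. Day 5 and every day from day 9 on lie in neither. SAP B filters on time alone, so an unscheduled test on, say, day 3 is not stated to be excluded. An unscheduled test on day 5 or day 12 is out because of its timing.

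**Step 2: can the Substudy A troponin text be programmed?** The data rule admits a day 5 result and the reporting line rejects it. Both cannot be applied, and nothing in the section says which prevails.

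**Step 3: where else would a late abnormal result appear?**
- *As an adverse event.* Protocol 10.3.1 requires an abnormal laboratory result to be recorded as an AE if it needs further diagnostic testing. Sections 10.11.8.8.10 and 10.12.8.10 require further evaluation of an abnormal troponin at Visit 2 or 3 (202 or 203), with or without symptoms. ECG findings enter as AEs if judged clinically significant. AEs through 4 weeks are also a primary endpoint.
- *In the cardiac symptom summaries.* Protocol 10.11.9.3.5.2 and 10.12.9.3.5, SAP A 6.6.1 and SAP B 6.5 cover 4 weeks, but only for participants with symptoms.
- *In extra Substudy B summaries.* Protocol 10.12.9.3.4 makes these optional.

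None of these puts the result back into the troponin or ECG row.

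**Step 4: the plan's own figure.** Protocol Table 9 gives the chance of seeing at least one event as 1 − (1 − p)^n. For p = 2%, 1 − 0.98^30 = 45.5% and 1 − 0.98^120 = 91.1%, as printed.

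**Step 5: one uncounted event, denominator unchanged.** Clopper-Pearson 95% limits, the method in SAP A and SAP B 5.2.1:

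| Group size | Event counted | Event not counted |
|---|---|---|
| 30 | 1/30 = 3.3% (0.1 to 17.2%) | 0/30 (0 to 11.6%) |
| 120 | 1/120 = 0.8% (0.02 to 4.6%) | 0/120 (0 to 3.0%) |

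**Step 6: other denominators.** SAP B 6.1.1.1 states a denominator for reactogenicity, but the troponin and ECG sections state none. If the participant with the late result also leaves the denominator, the row is 0/29, with upper limit 1 − 0.025^(1/29) = 11.9%. If instead the one event is in window and three participants with normal out-of-window results leave, the rate rises from 1/30 = 3.3% to 1/27 = 3.7%. The direction of the effect on the rate is therefore not fixed.

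**Step 7: range for the unknown share.** The documents give no out-of-window share. Assume a fraction q of participants is out of window and uncounted, independently of the result, and stays in the denominator. The chance of counting at least one event is then 1 − (1 − p(1 − q))^n. At p = 2%:

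| q | n = 30 | n = 120 |
|---|---|---|
| 0 | 45.5% | 91.1% |
| 5% | 43.8% | 90.0% |
| 10% | 42.0% | 88.7% |
| 20% | 38.4% | 85.6% |

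**The case against.** The best defence is that the AE route closes most of the gap. An abnormal troponin at a late Visit 202 is still a Visit 202 result. It triggers further testing, so Protocol 10.3.1 makes it an AE, and it counts in the primary 4-week AE rate and the coded AE tables. This stands. A reader might infer that a late abnormal result vanishes from the primary safety analysis, and the documents do not support that. What remains is that the AE tables depend on investigator recording and coding and do not correct a zero in the row named for that finding.

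Other stronger readings also fail:
- *A group could be paused and leave no trace in its primary tables.* The troponin stopping criterion needs confirmation on repeat testing and investigator-assessed relatedness. Such a finding would be a related AE. Stopping decisions do not rest on the windowed rate.
- *The windows cover only 6 of the 28 days.* The arithmetic is right (3 + 3), but the only scheduled post-dose troponins and ECGs are at the two visits, so most of those 28 days have no planned test.
- *The filter can only lower the rate.* It can only lower the event count. Step 6 shows that the rate can move either way.
- *Unscheduled tests are excluded.* SAP B does not say so for tests inside a window. In Substudy A the tie to Visits 2 and 3 points that way but is not explicit.
- *Substudy A counts only in-window troponins.* Its text supports both readings, so the point there is a contradiction.

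It is also fair to say that the study is descriptive, with no hypotheses, so no test or error rate is affected.

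**Conclusion.** The point holds in a limited form. In Substudy B a written rule removes abnormal troponin and ECG results on day 5 or from day 9 on from the named rates, with no sensitivity analysis to show what was removed. In Substudy A the troponin section gives two incompatible rules. Substudy A ECGs are not affected, and they show that the sponsor already uses an unfiltered count elsewhere.

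The size for a single event is 1/30 becoming 0/30 (or 1/120 becoming 0/120), on the assumption that the denominator stays the safety population. The overall effect cannot be given, because neither the out-of-window share nor the denominator is stated. With assumed shares of 5% to 20%, the loss in the chance of counting an event at a 2% true rate is modest: 1.7 to 7.1 percentage points at n = 30 (45.5% to 43.8% or 38.4%). The case for change rests on the clarity of a key safety row and on how little the change costs.

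**What to change.** In SAP B 6.1.3.1 and 6.1.4.1, and in SAP A 6.1.3.1:

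1. Drop the window as a condition for counting a result.
2. Assign each scheduled post-dose troponin (and, in Substudy B, each scheduled ECG) to its nominal visit, whatever the actual day.
3. State the denominator as participants with a result at that visit.
4. Add a supplementary row by vaccine group: *any abnormal troponin or new ECG abnormality after vaccination through 4 weeks, scheduled or unscheduled*. This follows the example of Protocol 10.11.9.3.5.1 for Substudy A ECGs.
5. Keep the in-window table as a sensitivity analysis.

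Step 2 also settles the Substudy A contradiction in favour of its stated treatment-policy strategy. The row in step 4 should be supplementary. A 4-week primary row would alter the protocol's 2-day and 1-week endpoint, and the protocol says that major changes to primary endpoint definitions must also go into an amendment.

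The cost is SAP wording in three sections, one added row and one retained table, with no change to conduct. The small downside is that visit-labelled rates will include a few off-schedule results.
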